9.3. Schedule of Events

Clinical data will be collected at the Baseline 3 month, 6 month, 12 month, and exit visits. In addition if applicable, clinical data will be collected with an exit or death, as well as unscheduled visits. Device data will be collected from device interrogations on Medtronic devices received during the period between the enrollment and exit until study closure; for non-Medtronic devices, device data will not be collected. Data will be collected using eCRFs using an electronic data management system for clinical studies. In addition to eCRF data, non-eCRF data will be collected including device interrogation files (for Medtronic implanted devices only). Surveys may also be used throughout the study.

Data will be stored in a secure, password-protected database, which will be backed up nightly. Data will be reviewed using programmed and manual data checks. Data queries will be made available to study sites for resolution. Study management reports will be generated by Medtronic to monitor data quality and study progress. At the end of the study, the data will be frozen and retained indefinitely by Medtronic. Data Collection requirements are summarized in the table 2 below.

Table 2 Data Collection and study procedure requirements at subject visit

Study Procedure	Baseline	3 month visit	6 month visit	12 month visit	Study Exit
Patient informed consent	X				
Eligibility Verification (Inclusion/ exclusion assessment)	X				
Subject Demographics	X				
Acute MI information	X				
Medical History	X				
Cardiovascular Medications	X	X			
LVEF measurement	X	X*	X (collect if performed as per SOC)	X (collect if performed as per SOC)	
ECG	X	X (collect if performed as per SOC)	X (collect if performed as per SOC)	X (collect if performed as per SOC)	
Referral Status		X	X	X	X
Implant Status (if applicable)		X (if subject receives or has received device implant)	X (if subject receives or has received device implant)	X (if subject receives or has received device implant)	X (if subject receives or has received device implant)
Device Interrogation File (pdd) or CareLink Transmission for subjects implanted with Medtronic device only		X	X	X	X
Adverse Event	As they occur				
System Modification					
Study Deviation					
Subject Death					

* The LVEF measurement needs to be performed ≥ 40 days post-acute MI for MI subjects without revascularization, or ≥ 90 days post-revascularization for post-MI subjects with revascularization done.

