  table referred/binomial (cl = wilson) alpha = 0.05 out = perc;
  ods output binomialCLs=percConf;
run;
```

The results will be shown for each region and overall in a table similar to the example table below:

Table 3: percentage (95% CI) of subjects referred for sudden cardiac death risk (SCD) stratification and management, among the subjects with at least one reason for referral at the 3 months visit (chronic phase)

Region	Proportion Referred	95% CI
Region 1	XX/XX (XX.XX%)	(XX.XX% - XX.XX%)
Region 2	XX/XX (XX.XX%)	(XX.XX% - XX.XX%)
...
Overall	XX/XX (XX.XX%)	(XX.XX% - XX.XX%)

A subject not referred for SCD risk stratification and management during their three months visit may later be referred. Thus, similar descriptive statistics may be generated at the 6 and at the 12 months post-baseline visits and displayed in a table similar to table 2 above.

Further, as part of an attempt to continually train the physicians on referring subjects with a reason for referral, periodic feedbacks on referral rates will be provided. Whether these periodic feedbacks will have an impact on referral rate will be investigated by producing, for each region and overall and over time, a penalized B spline plot. A SAS code similar to the below will be used:

```
ods graphics on / attrpriority=none;
proc sgplot data=referral noautolegend;
  title 'Penalized B-Spline for each region';
  styleatrrs datalinepatterns=(solid);
  pbspline y=prop x=time/group=region;
run;
```

Additional analyses may be provided and described in the final report.

Additionally to the analyses described above, logistic regression models might be used overall and by region, to estimate the odds ratios of referring patients for SCD stratification and management

depending on different factors, such as age, gender, LVEF≤40% versus any other reason for referral, physician's specialty, PCI versus non-PCI patients, STEMI versus non-STEMI patients. An example SAS code similar to the below will be used:

```
proc logistic data = referral;
  by region;
  class factor/descending;
  model referred (event = '1') = factor/expb;
  oddsratio factor;
  ods output ParameterEstimates = ParEstim;
  ods output OddsRatiosWald = OREstim;
run;
```

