where referred is the outcome and is equal to 1 if the subject has been referred and 0 otherwise, factor is the independent factor of interest (eg: reason for referral, physician's specialty). Results of the logistic regression model will be displayed by means of either tables or plots.

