It may also happen that a patient might have an SCD risk stratification visit without having been referred, for example, patients who had an SCD risk stratification visit for secondary prevention. An additional table will then be created to show, for each visit, the number of subjects that were not referred but had an SCD risk stratification visit and among those, the proportion of subjects that had a reason for referral.

Second, the proportion and Wilson score 95% CI of subjects recommended for ICD/CRT-D at the three months visit, at the 6 months and at the 12 months visits will be computed overall and by region, for the Enrolled Population and for the subjects in the numerator in table 3 above, that is, all subjects that have had an SCD risk stratification visit (called in table 4 below “SCD risk stratification Population””).

A SAS code similar to the example SAS code shown in Section 7.9.1.3 will be used. For each follow up visit, the results will be shown in a table similar to Table 5 below.

Table 5: Proportion (95% CI) of subjects indicated to receive ICD/CRT-D, at visit X

Region	Enrolled Population		SCD risk stratification population	
	n/N (%)	95% CI	n/N (%)	95% CI
Region 1	XX/XX (XX.XX%)	(XX.XX% - XX.XX%)	XX/XX (XX.XX%)	(XX.XX% - XX.XX%)
...
Overall	XX/XX (XX.XX%)	(XX.XX% - XX.XX%)	XX/XX (XX.XX%)	(XX.XX% - XX.XX%)

Where n is number of the subjects “recommended for ICD/CRT-D” and N is either the Enrolled Population or the SCD risk stratification population.

In addition to the above analyses, logistic regression models similar to the example model in Section 7.9.1.3 might be fitted overall and by region, to estimate the odds ratios of being indicated for an ICD/CRT-D, depending on different factors, such as sex, age, specialty of physician who performed the ICD/CRT-D risk stratification, type of device received – ICD or CRT-D, PCI versus non-PCI patients, STEMI versus non-STEMI patients . Results will be displayed either by means of either tables or of plots.

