7.9.3.3 Analysis methods

At each follow-up visit (3 months, 6 months, 12 months), the proportion of subjects who received an ICD/CRT-D will be computed.

The numerator will be the number of subjects who were implanted at a given follow up visit. In the Implant CRF, these subjects will have answer “yes” to the question “Has the subject received an ICD or CRT-D?”.

The denominator will be either the Enrolled Population or a composite of the below:

- (a) ***all patients meeting an indication for implant and not having been implanted at the previous visits.*** That is, within the Implant CRF form, all subject that at any previous visits will have answer “yes” to the question “did the subject meet an indication for an ICD or CRT-D?”, and at all previous visits will have answer “no” to the question “has the subject received an ICD or CRT-D?”
- (b) ***all patients meeting an indication for implant at the given visit.*** That is, within the referral CRF form, all subject that at a given visit will have answer “yes” to the question “did the subject meet an indication for an ICD or CRT-D?”

A SAS code similar to the example SAS code shown in Section 7.9.1.3 will be used. Separately for each follow up visit, the results will be shown in a table similar to Table 6 below, where “Indicated for an ICD/CRT-D” is the denominator above.

Table 6: Proportion (95% CI) of subjects who receive ICD/CRT-D at visit X

	Enrolled Population		Indicated for an ICD/CRT-D Population	
Region	n/N (%)	95% CI	n/N (%)	95% CI
Region 1	XX/XX (XX.XX%)	(XX.XX% - XX.XX%)	XX/XX (XX.XX%)	(XX.XX% - XX.XX%)
Region 2	XX/XX (XX.XX%)	(XX.XX% - XX.XX%)	XX/XX (XX.XX%)	(XX.XX% - XX.XX%)
...
Overall	XX/XX (XX.XX%)	(XX.XX% - XX.XX%)	XX/XX (XX.XX%)	(XX.XX% - XX.XX%)

In addition to the above analyses, logistic regression models similar to the example model in Section 7.9.1.3 might be fitted overall and by region, to estimate the odds ratios of being implanted, depending on different factors, such as age, gender, specialty of physician who implanted, type of device received – ICD or CRT-D, PCI versus non-PCI, STEMI versus non-STEMI. Results will be displayed either by means of either tables or of plots.

Additional analysis:

A competing risk event curve with accompanying 95% confidence bounds and mortality accounted for, will be produced for each region, to assess a subject's time from enrollment to:

- (a) Having met the referral criteria;
- (b) Having been referred;

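### SAP 7.9.3.3 and 7.9.2.3 list factors that exist only after implant as predictors of being implanted or indicated; odds ratios for those factors are not estimable or not interpretable

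*SAP*

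**What the plan says.** SAP 7.9.3.3 (secondary objective 2) adds optional logistic regressions, overall and by region, "to estimate the odds ratios of being implanted, depending on different factors, such as age, gender". The list of example factors continues with "specialty of physician who implanted, type of device received", then PCI and STEMI status.

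SAP 7.9.2.3 (secondary objective 1) has a parallel paragraph, "to estimate the odds ratios of being indicated for an ICD/CRT-D, depending on different factors". Its list includes "specialty of physician who performed the ICD/CRT-D risk stratification, type of device received". The physician named here is the one who did the risk stratification, not the implanter.

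Both sections refer to the example code in SAP 7.9.1.3, whose model statement is "model referred (event = '1') = factor/expb". The accompanying text says "factor is the independent factor of interest (eg: reason for referral, physician's specialty". The template therefore regresses a yes/no outcome on one classification factor at a time.

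For the outcome, SAP 7.9.3.3 identifies implanted subjects from the Implant CRF: "these subjects will have answer “yes” to the question “Has the subject received an ICD or CRT-D". In Protocol Table 2 (section 9.3) the entry for implant status at each follow-up visit is "X (if subject receives or has received device implant". Protocol 12.5 rules out imputation, and SAP 7.4 says that the main analyses make no allowance for missing data.

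**The concern.** A predictor of an outcome needs a value both for subjects who have the outcome and for those who do not. A subject without a device has no implanting physician and no device type. In the implant model these two factors therefore restate the outcome. In the indication model, device type is a later event used to explain an earlier one.

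The Protocol's background gives understanding low ICD use as a reason for the study, so which physicians and patients are linked to implant is a natural question. For these factors the models cannot answer it. The risk is an analysis that fails when run, or a meaningless odds ratio that reaches a report table.

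**Working it through.** **The plan's own figure.** The documents give no design figure for the logistic models. The only one is the 54 subjects per region with a reason for referral (SAP 6.1), used below just to set a realistic size. It reproduces. The Wilson half-width is z/(1 + z²/n) × √(p(1−p)/n + z²/(4n²)). The exact binomial probability that it is at most 0.125, at a true proportion of 0.70, is 0.784 for n = 53 and 0.897 for n = 54, so 54 is the smallest n reaching 0.80. Then 54/0.30 = 180 and 180/0.90 = 200.

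**Implant model: the table that the template would fit.** Let N subjects include k implanted, of whom k₁ received one device type and k₂ the other (k₁ + k₂ = k).

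| Factor level | Implanted | Not implanted |
|---|---|---|
| Type 1 | k₁ | 0 |
| Type 2 | k₂ | 0 |
| No value | 0 | N − k |

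- *Last row missing and dropped.* The odds ratio of type 1 against type 2 is (k₁ × 0)/(0 × k₂) = 0/0, which is undefined. Only one outcome level remains.
- *Last row coded as none.* The odds ratio of type 1 against none is k₁ × (N − k)/(0 × 0), which is unbounded. This is complete separation. Type 1 against type 2 is still 0/0.

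Implanter specialty gives the same table with specialties in place of device types.

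**Trial fits on made-up data.** N = 54; the numbers implanted and their split by type are assumptions.

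| Implanted (split) | Dropped: outcome yes / records left | Coded none: log odds ratios against none (standard errors) |
|---|---|---|
| 5 (2, 3) | 5/5 | 46.9, 47.3 (62,568; 62,127) |
| 10 (6, 4) | 10/10 | singular matrix |
| 20 (11, 9) | 20/20 | 55.7, 63.1 (454,097; 22,370,127) |
| 30 (18, 12) | 30/30 | 69.2, 77.8 (1.86 × 10⁸; 1.87 × 10⁸) |

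These values show only where the algorithm stopped. In the 30-implant case with the other records dropped, the routine still printed a coefficient of −9.7 with a standard error of about 15,546, so software may return a number where no estimate exists. The zeros are structural, so enrolling more subjects does not remove them.

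**Indication model with device type.** SAP 5.1 expects implant to follow indication and referral. If every implanted subject is indicated, every subject with a device type has outcome yes. In an assumed example (54 subjects, 30 indicated, 12 of them implanted), 12 of 12 remaining records have outcome yes.

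**Where variation could arise.** SAP 7.9.3.3 counts implants at a given visit, and one of its denominators is the whole Enrolled Population. At 6 or 12 months, a subject implanted earlier has a device type but is outside that visit's numerator. An odds ratio could then be computed, but it would contrast when implanted subjects got their device, not whether subjects got one. In the indication model, an implant without a recorded indication would likewise allow a number, conditional on having been implanted.

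**The case against.** The strongest reply is that little depends on these models. They are optional, the factor lists are illustrative, the objectives carry no hypothesis, and SAP 7.5 calls the study exploratory. The committed results for these objectives are the Table 5 and Table 6 proportions and the competing-risk curves, none of which uses the listed factors. A failed fit would probably be noticed, and SAP section 9 requires changes to be justified in the report. All of this stands and makes the point minor. It does not make the factors usable: they are named explicitly, and a programmer following the SAP would try them.

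A second reply is that the authors meant the device type *indicated*. The text says received in both sections. In 7.9.2.3 an indicated type would have the same fault, because it exists only for indicated subjects.

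A reader might also infer more than the documents support:

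- *That all odds ratios in these models fail.* The template takes one factor per model, so age, sex, PCI and STEMI are unaffected. Only if a post-implant factor were entered jointly with them would the model collapse to implanted subjects.
- *That implanter specialty is in both models.* It appears only in 7.9.3.3.
- *That the stratifying physician's specialty in 7.9.2.3 has the same fault.* It is known for everyone who had the stratification visit. That group is already one of the two denominators in Table 5, and indication can vary within it.
- *That the odds ratios can never be computed.* Visit-specific outcomes or unrecorded indications could yield numbers. The fault is then one of meaning.

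**Conclusion.** The point holds for three entries: implanter specialty and device type received in SAP 7.9.3.3, and device type received in SAP 7.9.2.3. For the implant model the failure follows from the definition of the factors and needs no data. With outcome taken as ever implanted, all subjects with a factor value have the event. For the indication model it rests on the expectation that implanted subjects have a recorded indication. The documents contain no data on how often that is so, so no proportion should be quoted.

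The size is small. The primary analysis, the sample size and the committed secondary estimates do not change. It is a minor correction to named analyses that cannot answer their question as written.

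**What to change.** In the SAP:

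1. Delete implanter specialty and device type received from the factor list in 7.9.3.3, and device type received from the list in 7.9.2.3.
2. State that factors in these models are limited to those known before the outcome.
3. State that the stratifying physician's specialty in 7.9.2.3 is fitted only within the SCD risk stratification population.
4. Report device type and implanter specialty as counts and percentages among implanted subjects.

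The cost is a few lines of SAP wording. No new data are needed, and the Protocol's statistical section does not mention these models, so the change can be confined to the SAP.

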7.2 General Methodology

Data summaries for categorical data will include count, e.g., number of patients, and/or number of events, and a percentage relative to the total number of patients/events. The denominator will be explicitly identified when not clear from the context. Continuous variables will be represented by mean and standard deviation, except when the distribution of the variable is highly skewed in which case median and quartiles will be reported.

P-values for hypothesis testing will be evaluated based on two-sided testing using significance level of 0.05. Confidence intervals will be reported as two-sided 95% confidence intervals.

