- (c) Having had an SCD stratification visit;
- (d) Having been indicated an ICD/CRT-D implant
- (e) Having received an ICD/CRT-D.

An SAS code for the competing risk analysis similar to the below will be used:

```
proc lifetest data=KM plots=cif(test) timelist=0 1 2 3 4 5 6 7 8 9 10 11 12;
  by region;
  time T*Status(0) /eventcode=1;
  strata Event / order=internal;
run;
```

where Event is a categorical variable with categories the event of interest (meeting the referral criteria, having been referred, having had an SCD risk stratification visit, having been indicated for an ICD/SCD-D implanted, having received an ICD/CRT-D), T is the time in months from enrollment to the date of the event of interest and Status is an indicator variable with 3 values: 0 for censored observations, 1 observations related to the event of interest and 2 observations related to subjects who died. Note that the dataset to be used will contain one row for each event per subject (e.g.: if a subject will have all events, from having met the referral criteria to having received the ICD/CRT-D, the dataset will contain 5 rows for that subject).

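### The example competing-risk code in SAP 7.9.3.3 requests a test across five milestones recorded on the same subjects; any p-value it prints is invalid and should be suppressed (low priority)

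*SAP*

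**What the plan says.** SAP 7.9.3.3, under its additional analysis, describes the output this way: "A competing risk event curve with accompanying 95% confidence bounds and mortality accounted for, will be produced for each region". The times run from enrolment to each of five milestones: referral criteria met, referred, SCD stratification visit held, indicated for a device, device received. No comparison between milestones is mentioned.

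The example code is more specific. It opens with "proc lifetest data=KM plots=cif(test", so the plot carries the `test` option, and it then sets "strata Event / order=internal". The explanatory text says that "Event is a categorical variable with categories the event of interest", and that death is the competing event, coded as "2 observations related to subjects who died". The data are stacked: "the dataset to be used will contain one row for each event per subject". For a subject who passes every milestone, "the dataset will contain 5 rows for that subject".

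Elsewhere, SAP 7.9.3.1 states that this objective has no hypotheses, and SAP 7.4 states that none of the objectives involves hypothesis testing. SAP 7.2 nevertheless sets a general rule: "P-values for hypothesis testing will be evaluated based on two-sided testing using significance level of 0.05".

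**The concern.** A test between strata of a competing-risk analysis compares separate groups of people. Here the strata are types of event, and the same people appear in all of them. There are two distinct faults.

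- **Dependence.** The variance of the test statistic treats the strata as independent samples. Nothing in the code identifies the subject, so the link between one person's five rows is ignored.
- **No useful null.** The milestones mostly follow one another. Five identical curves would require essentially everyone who meets the criteria to go on to implant, with hardly any delay. Rejecting that says only that some patients do not progress, which the curves already show.

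What is at stake is a p-value on the pathway figure of each region that answers no planned question. The 0.05 rule in SAP 7.2 would invite a reader to interpret it.

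**Working it through.** **Inputs from the SAP.** About 200 subjects per region (5.1). Exit or death before 3 months 10%, a reason for referral 30%, referral given a reason 70% (6.1). Five milestones, stacked by subject, with death as the competing event (7.9.3.3).

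**Step 1: reproduce the plan's own figure.** The SAP gives no figure for this test, so only the 200 can be checked. With p = 0.70, the exact binomial probability that the Wilson 95% half-width is at most 0.125 is 0.784 at n = 53 and 0.897 at n = 54. So 54 is the first n to reach 80%. Then 54/0.30 = 180 and 180/0.90 = 200. Both figures reproduce.

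**Step 2: are equal curves plausible under the plan's assumptions?** Of 200 enrolled, 54 have a reason for referral at 3 months and 54 × 0.70 = 37.8 are referred. The first two curves would then stand near 54/200 = 27% and 37.8/200 = 18.9% at that visit. The plan itself expects the curves to differ.

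**Step 3: the test statistic.** A five-sample Gray-type test was simulated, keeping subjects who die in the risk set. At each event time t, let Y_k be the number at risk in stratum k, R = ΣY_k, and D the events in all strata. Then:

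- O_k = events in stratum k; E_k = Σ_t Y_k·D/R; u_k = O_k − E_k
- V_jk = Σ_t [D(R − D)/(R − 1)]·[δ_jk·Y_k/R − Y_j·Y_k/R²], where δ_jk is 1 if j = k and 0 otherwise
- X² = u′V⁻¹u with one stratum dropped, referred to chi-square on 4 df

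V has no term for the same subject appearing in several strata. Censoring was administrative at 12 months only.

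**Step 4: rejection when the five marginal curves are equal.** Assumed, not from the SAP: a 30% event probability by 12 months in the absence of death (monthly rate −ln(0.70)/12) and 10% mortality over 12 months (monthly rate −ln(0.90)/12). There were 200 subjects, 1,500 runs and a nominal level of 0.05. The Monte Carlo standard error at 5% is √(0.05 × 0.95/1500) = 0.56 percentage points.

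- Five independent samples of 200: 5.2%
- Same subjects, within-subject correlation 0: 4.2%
- Correlation 0.25: 2.1%
- Correlation 0.50: 0.5%
- Correlation 0.75 or more: 0%

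The test holds its level when the samples really are independent. When the same subjects are stacked with positive correlation, it is conservative. Differences between curves on the same people vary less than V supposes.

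**Step 5: rejection along an ordered pathway.** 30% meet the criteria, at a time uniform between 1 and 4 months. Each later step has the pass probability shown and an exponential delay with mean 0.1 or 0.5 month. Mortality is as in step 4, with 500 runs per cell. The 30%, and the 70% referral in the first two rows, are the SAP's values applied to all enrolled subjects; the rest is assumed.

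| Referral / visit / indicated / implanted | Rejection, delay 0.1 | Rejection, delay 0.5 |
|---|---|---|
| 70 / 70 / 70 / 50% | 100% | 100% |
| 70 / 90 / 90 / 90% | 96.6% | 99.6% |
| 90% at every step | 38.0% | 74.6% |
| 95% at every step | 0% | 4.6% |
| 100% at every step | 0% | 0% |

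The p-value follows the assumed attrition. It carries no information beyond the curves, and its level is wrong in any case.

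**The case against.** The strongest reply is that no test is planned. The prose asks for curves with bounds, SAP 7.4 and 7.9.3.1 rule out hypothesis testing for this objective, and SAP 7.5 calls the study exploratory. The code is an example that the final program need only resemble. The cardiovascular mortality code in SAP 7.9.4.3 carries the same plot option with no STRATA statement, so it has no groups to compare. That suggests a reused template rather than a chosen inference. Using STRATA to overlay curves is ordinary practice. All of this stands, and it is why the point ranks low. It does not rescue the code, which contradicts the prose and will be a programmer's starting point. SAP section 10 allows self-validation for non-primary outputs, so independent review may not catch it.

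Three stronger readings are tempting but not supported.

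- A reader might infer that 200 × 5 = 1,000 rows inflate the sample size and so produce false positives. Step 4 shows the opposite under equal curves.
- A reader might infer that the p-value is bound to be significant. Step 5 shows that this depends on attrition, and the SAP gives no rates for the steps after referral.
- A reader might infer that the sponsor intends to draw a conclusion from the test. No text in SAP 7.9.3 does so, and the 0.05 rule in SAP 7.2 covers hypothesis tests, of which this objective has none.

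Nor can the curves be declared sound without a condition. The row rule can be read as giving a subject a row only for events that occurred. On that reading the risk sets, and hence the curves, would be wrong.

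**Conclusion.** The point holds in a limited form. Run as written, the code requests a between-strata test whose independence assumption fails and whose null has no useful meaning. It also conflicts with the SAP's own text, which plans no test here. The invalidity follows from the design of the dataset and needs no simulation. The size of the error does depend on assumptions: rejection runs from 0% to 100% across the scenarios above, with 97-100% at 70% referral and later steps of 50-90%.

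The five curves and their pointwise 95% bounds are unaffected by this fault, provided every subject contributes one row (event, death or censored) to each stratum. The primary endpoint, the sample size and every planned interval are untouched. Priority is low.

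**What to change.** In the SAP 7.9.3.3 example code, remove `(test)` from the plot request and suppress the between-strata test in the rest of the output. Keep Event as a stratum for display only, so that the five curves stay on one figure. If separate plots are acceptable, sorting and running by region and Event in place of the STRATA statement serves equally well. Add a sentence that no p-value comparing milestones will be reported. If such a comparison is ever wanted, it needs a method that resamples or clusters by subject.

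In the same edit, state that each subject has one row in every Event stratum, whether the outcome is the event, death or censoring.

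No all-region set of curves is needed for this fix: the SAP asks for these curves by region. The cost is a small edit to example code and two sentences, best made before programming starts. Nothing changes in data collection or sample size.
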